11.5. Interim analysis

There is no planned interim analysis in this investigation that will affect the evaluation of the primary objective. To facilitate the evaluation of the secondary objective regarding evaluation of the [REDACTED] [REDACTED] a data migration will be provided to the external partner [REDACTED] before DBL. The data migration will be based on data from all subjects having finalized visit 2. Any results of the analyses of data from [REDACTED] before DBL will be for the use of [REDACTED] only and not reported to Coloplast A/S.

11.6. Statistical reason for termination of investigation

There will be no interim analysis and therefore no reason to terminate the investigation based on statistical considerations.

11.7. Deviation(s) from statistical design, method or analytical procedures

Any deviations from the statistical plan will be documented in the clinical investigation report.

12. Data collection and data management

12.1. Data Collection in the clinical investigation

Data will be collected through an electronic data capturing system on the eCRF, a secure, internet-based case report form. This system will be used to record all subject information collected in the investigation for secure data tracking and centralised data monitoring ("remote monitoring") done by monitors, as defined in the monitoring plan.

The data management system is delivered by Medidata Solutions and is named Rave. Current version number is version 2018 2.2. The system is designed for electronic data capture, and it is compliant with the requirements of 21 CFR part 11. It is a validated data management system allowing only qualified and trained personnel to enter the system. The system has full audit trail and electronic signature.

Principal Investigator, or delegate, at the clinical site will perform primary data collection directly into the eCRF or drawn from source-document (medical records) reviews. These data will be uploaded to the data base on a continuously basis. The electronic CRF will be completed on a continuous basis starting from the point of enrolling the subject to final follow up. The sponsor, or delegate, will provide clinical monitoring, including review of eCRF with verification to the source documentation, as defined in the monitoring plan.

The subject will receive a smartphone with the Clinical Trial App installed. The app is developed on behalf of Coloplast A/S by the app development company [REDACTED]. This Clinical Trial App is used during the investigation every time the subject makes a product (1pc) or baseplate (2pc) change.

All data must be recorded in the eCRF during the visit or immediately after.

12.2. Database Management and Quality Control

The data management system has restricted role-based access control. The principal investigator or delegate must be trained in the system prior to getting access. The training is web-based and must be completed before

CONFIDENTIAL

access to the investigation is granted. Training will be documented in the data management system. Only the principal investigator, or delegate, will be authorised to enter data in the eCRF,

The principal investigator can delegate tasks to his/her collaborators, however the roles and responsibilities as time period of involvement for each clinical site personnel must be documented on the delegation log as well as training received before getting involved with the clinical investigation must be documented in the training log.

The monitor, using his/her personal login information shall verify all critical data points against the source documents and issue electronic queries for the authorised clinical site personnel to respond, as defined in the monitoring plan.

The principal investigator, using his/her personal login information shall sign each case report form in the EDC system.

Automated, real time access to the data enable control on study compliance and safety assessments. Automated alerts (emails) are generated by the system to ensure full control and easier compliance to the clinical investigation plan.

A critical quality control will be performed by the sponsor's data management team and queries issued where needed. Such queries will be reviewed by the monitor and released in the system as a query to be resolved by the site personnel.

At the end of the study a formal data review meeting will be performed before the database will be locked.

A full audit trail ensures, that each user (site personnel, monitor, sponsor, data manager) access to the system is tracked, so that all data operations can be followed for monitoring and verification.

The photos and the data completed in the Clinical Trial App are transferred via an encrypted connection to a Coloplast controlled [REDACTED] environment. Photos will be stored and can be assessed at [REDACTED] All other data will be transferred automatically into the data management system.

12.3. Data review, database cleaning, and issuing and resolving data queries

Data management and the final statistical analyses of all measurements described in this protocol are carried out by the, Medical Affairs, Coloplast A/S. The evaluation of the [REDACTED] [REDACTED] is carried out by [REDACTED] according to the SAP.

12.4. Data retention

The sponsor file must be archived for a minimum period of ten years after the final investigation report has been signed. All site documents must be archived for a minimum period of ten years after the final clinical investigation report has been signed.

13. Amendments to the CIP

No changes in the clinical investigation procedures shall be affected without mutual agreement of the principal investigator and the sponsor. The agreement of the changes must be documented by signing the corresponding clinical investigation plan amendments. All changes must be registered in the Change Log with a rationale.

CONFIDENTIAL

All changes require notification to the EC and the CA (when appropriate). Substantial changes may require approval from the EC and the CA prior to implementation.

14. Deviations from Clinical Investigation Plan

Every effort should be made to avoid deviations from the clinical investigation plan during the conduct of the investigation. The Investigator is not allowed to deviate from the CIP unless under emergency circumstances and to protect the rights, safety and well-being of the subject(s). Deviations must be reported to sponsor and deviations affecting the scientific aspect of the investigation or the safety of the subject (violation) are reported to the EC and regulatory authorities by sponsor if required by national regulations.

For reporting purposes, the sponsor classifies study deviations as major and minor:

Major deviation: Any deviation that may either have an impact on the rights, safety and well-being of the subjects or the scientific outcome of the clinical investigation.

Minor deviation: Any deviation that has no impact on the rights, safety and well-being of the subject or that may impair the scientific outcome of the clinical investigation.

The Investigator should inform the CM/CRA of any deviation, and the implications of each deviation must be reviewed and discussed. If the deviation affect the subject, discussion for a decision on the further participation of the subject should be completed. Any deviation must be documented, stating the reasons, date, actions taken, and the impact for the subject and/or investigation. This documentation must be kept either in the Deviation Log in the Investigator Site File or in the Deviation CRF form, depending on the deviation's relation to either the data collected in the CRF or all other case of any deviations on site.

Deviations occurring outside of the investigation site, by vendors will be documented by the Sponsor.

15. Accountability of investigational products

All access to the investigational products (non-CE marked investigational product and CE marked comparator investigational products) used in the clinical investigation is controlled by storage procedures and accountability logs as described below. The Coloplast investigational product must only be used in this clinical investigation and only according to the CIP.

Sponsor keeps an accountability log that states the physical location of all investigational products from shipment of investigational products to the investigational sites until return of or disposal.

The PI or delegate keeps records documenting the receipt, use and return and disposal of the investigational products, which includes:

- Name of the product received
- Date of receipt.
- Identification of each investigational products (batch no./lot no.)
- Number of products received
- Number of products distributed to subject
- The date(s) of use
- Subject identification
- The date on which the investigational product was returned/explanted from the subject
- The date of return unused, expired or malfunctioning investigational products to Sponsor

CONFIDENTIAL

16. Statement of compliance

The clinical investigation is conducted in accordance to:

- Ethical principles that have their origin in the Declaration of Helsinki, 1964, Last amended at the 59th WMA General Assembly, Brazil, October 2013.
- MDD 93/42/EEC as amended by Directive 2007/47/EC (commonly known as the Medical Device Directive).
- ISO 14155:2011 "Clinical Investigation of medical devices for human subjects – Good clinical practices".
- Any applicable regional or national regulations will be specified in the country specific CIP.

16.1. Ethics committee and regulatory authorities

The CIP and/or other relevant documents are submitted to the appropriate EC(s) and regulatory authorities. This clinical investigation will not begin until the required approval from the EC and regulatory authorities have been obtained. Any amendment to the protocol will be submitted to the same EC(s) and regulatory authority.

Sponsor will notify the relevant regulatory authority and EC(s) concerned of the end of the clinical investigation.

16.2. Data protection

As part of the investigation Coloplast A/S, [name] ("Coloplast") will collect and process the personal information that the subjects provide for the investigation ("personal data"). This includes identification and contact information (which will be anonymised) as well as information about product usage experience and health. Coloplast will only process personal data:

1. To conduct the investigation and carry out related research based on the subjects consent (primary use), cf. article 9(2)(a) of the EU General Data Protection Regulation (GDPR),
2. To comply with applicable legal obligations to e.g. ensure reliability and safety, cf. article 6(1)(c) in conjunction with article 9(1)(i) of GDPR, and
3. If separate consent is given for secondary use of your personal data, cf. article 9(2)(a) of GDPR –carry out research outside the clinical protocol to improve Coloplast's products and services, and for use in education.

Part of Coloplast's processing is carried out on third-party platforms (clinical trial databases) and certain third parties are assisting Coloplast in the processing (e.g. the investigator). Such cases will imply a transfer of personal data to the third parties, but solely for the specified purposes and with the third parties acting on instruction from Coloplast. Data may be collected and processed across the Coloplast network, which may entail processing of personal data outside the European Economic Area. In such cases, an adequate level of protection will be ensured by the third parties being subject to the standard contractual clauses on data protection adopted by the EU or to an EU-approved certification mechanism on data protection. For further information about this please consult Coloplast's data protection officer (details below).

Personal data will be kept as long as required under applicable laws and regulations. The EU Medical Device Regulation obligates Coloplast to keep the data for a period of at least ten years after the investigation is completed, or, in the event that the device is subsequently placed on the market, at least ten years after the last device has been placed on the market. Personal data will be deleted at the end of the mandatory retention

CONFIDENTIAL

period. If the subject wish to learn more about how Coloplast processes personal data, they can visit www.coloplast.com/global/privacy-notice.

If the subject have questions or queries regarding Coloplast's handling of personal information, they must contact Coloplast's Data Protection Officer at [REDACTED] Complaints related to Coloplast's handling of personal information may similarly be sent to the Data Protection Officer, and subjects are also entitled to file a complaint with the relevant supervisory authority, which in the case of Denmark is the Danish Data Protection Agency (www.datatilsynet.dk).

Subjects can write to [REDACTED] at any time to request:

1. Access to their data
2. Correction of errors in their data or to erase their data
3. Limit what can be done with their data
4. To receive their data in machine-readable format (data portability).
5. Withdrawal of consents they have given Coloplast to process their data

16.3. Financial conditions

16.3.1. Investigator payment

Coloplast A/S will compensate all principle investigators involved in the clinical investigation for their time and resources spent on the investigation. All financial agreements with the investigation sites involved in the clinical investigation will be specified in a sponsor investigator agreement.

16.3.2. Subject compensation

The subject will receive payment for their participation in the investigation. They will be paid cash in local currency based on the below numbers. The compensation is taxable, according to national regulations. In addition, the subjects will be compensated for transportation to the site. The

Subject payment/subject/visit

16.3.3. Compensation in case of injury

Product liability and No-Fault Clinical Investigation Insurance covering the duration of the clinical investigation are in place, to enable compensation in the event of an injury to a participating subject.

CONFIDENTIAL

17. Informed consent process

Written informed consent is obtained from all subjects participating in the investigation after thorough written and verbal information. The information is given by the principal investigator, or delegate in the subjects' native non-technical language. Each subject will be fully informed about the aim of the investigation, procedures, potential risks or inconveniences and/or expected benefits. The subjects will be informed that their participation is voluntary and that they may leave the investigation at any time, without this having any influence on their further treatment.

The informed consent signature form includes personally dated signatures of the subject and the principal investigator, or delegate responsible for conducting the informed consent process. A copy will be provided to the subject.

If new information is to be given during the investigation, sponsor will inform the principal investigators, and the new information is given to the subjects by the principal investigator. If new information becomes available that can significantly affect a subject's future health and medical care that information will be provided to the subject in written form. Clinical manager is responsible for writing the information and providing it to principal investigators that will further provide it to the subjects. If applicable, all affected subjects shall be asked to confirm their continuing informed consent in writing.

This procedure also applies to informed consent obtained from a subject's legal representative. The procedure cannot waive the subjects' legal rights.

18. Adverse events, adverse device effects and device deficiencies

18.1. Adverse events

An adverse event is any untoward medical occurrence, unintended disease or injury, or untoward clinical signs (including abnormal laboratory findings) in subjects, users or other parties, whether or not related to the medical device(s), or the procedures involved. This could include events such as headache or dizziness.

18.2. Adverse device effect

An adverse event, which is related to the use of the investigational medical device, is an adverse device effect, and should be marked as related or possibly related on the adverse event form.

The definition of an adverse device effect includes any event resulting from insufficiencies or inadequacies in the instruction for use, or any malfunction of the medical device, as well as any event resulting from use error or from intentional misuse of the device.

18.2.1. Anticipated device effects

Temporary redness upon removal of the baseplate is not considered to be an adverse device effect. However, an abnormal development in the intensity or duration of redness should be considered an adverse device effect. A development in redness after removal of the baseplate is considered abnormal, when the intensity of redness is not decreased after five-ten minutes after the baseplate has been removed.

18.3. Device deficiency

A device deficiency is the inadequacy of the investigational medical device or comparator with respect to its identity, quality, durability, reliability, safety or performance. This includes malfunctions, use errors and inadequacy in the information supplied by the manufacturer including labelling.

CONFIDENTIAL

Example: A 1pc. stoma bag is badly adhered to the baseplate and induce leakage of output.

18.4. Serious adverse events (SAE)

A serious adverse event is an adverse event that:

- Led to death,
- Led to a serious deterioration in the health of the subject, users or other persons as defined by one or more of the following:
 - 1) a life-threatening illness or injury, or
 - 2) a permanent impairment of a body structure or a body function including chronic diseases, or
 - 3) in-patient or prolonged hospitalization, or
 - 4) medical or surgical intervention to prevent life-threatening illness or injury or permanent impairment to a body structure or a body function.
- Led to fetal distress, fetal death or a congenital abnormality or birth defect.

This includes device deficiencies that might have led to a serious adverse event if:

- Suitable action had not been taken, or
- Intervention had not been made, or
- Circumstances had been less fortunate.

These are handled under the serious adverse event reporting.

Planned hospitalization for a pre-existing condition, or a procedure required by the CIP, without serious deterioration in health, is not considered a serious adverse event.

18.4.1. Serious adverse device effect (SADE)

A serious adverse device effect is an adverse device effect that has resulted in any of the consequences characteristic of a serious adverse event.

18.4.2. Anticipated serious adverse device effect (ASADE)

Anticipated serious adverse device effect is any event that by its nature, incidence, severity or outcome has been previously identified in the risk analysis report.

18.4.3. Unanticipated serious adverse device effect (USADE)

An unanticipated serious adverse device effect is a serious adverse device effect which by its nature, incidence, severity or outcome has not been identified in the current version of the risk analysis report.

18.5. Medical care of subjects

Principal investigator shall ensure that adequate medical care is provided to a subject experiencing an adverse event during and after participation in the clinical investigation. All serious adverse events will be followed until a resolution is addressed.

The current status of all ongoing adverse events is documented during site close-out.

CONFIDENTIAL

18.6. Reporting and timelines

18.6.1. Investigator's reporting responsibilities

- PI, or delegate, at each site must assess all (S)AE's that occur at his/her site.
- All serious adverse events and serious adverse device effects must be reported to sponsor within 24 hours of the site becoming aware of the event.
- A device deficiency that could have led to a serious adverse event but did not because suitable action was taken, intervention had been made or because of fortunate circumstances should be reported to sponsor within 24 hours of the site becoming aware of the event.
- New findings and/or updates in relation to already reported serious events should also be reported to sponsor within 24 hours of the site becoming aware of the event.
- Device deficiencies and all adverse device effects must be reported to sponsor within 10 days of becoming aware of the event.

When reporting the events, the relationship to the Investigation product and the intensity of the event shall be described whether the event is considered

- **Not related**, the event has no temporal relationship with the use of the test material or the procedures.
- **Unlikely related**, the relationship with the use of the test material seems not relevant and/or the event can be reasonably explained by another cause, but additional information may be obtained.
- **Possibly related**, the relationship with the use of the test material is weak but cannot be ruled out completely. Alternative causes are also possible (e.g. an underlying or concurrent illness/ clinical condition or/and an effect of another device, drug or treatment). Cases where relatedness cannot be assessed or no information has been obtained should also be classified as possible.
- **Probably related**, the relationship with the use of the test material seems relevant and/or the event cannot reasonably be explained by another cause, but additional information may be obtained.
- **Definitely related/Causal relationship**, the event has a temporal relationship with the test material use/application or procedures.

or the event is considered

- **Mild**, the intensity of the event is mild with no further action or intervention
- **Moderate**, the intensity of the event will lead to an action or intervention to solve the event
- **Severe**, the intensity of the event will lead to follow up on the action or intervention, as the effect of the action or intervention may not decrease the symptoms.

All above events must be reported by use of the relevant adverse event/serious adverse event/device deficiency form.

Please report to:

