5.1.6. Total number of investigational products intended for the clinical investigation

The subjects will be included for 42^{±3} days per test period, for a total of up to 90 days.

Subjects using 1-piece products are expected to change their products every day. Therefore, they are expected to use 45 test products and 45 comparator products during their participation.

Two-piece users are expected to use two baseplates every three days. Therefore, they are expected to use 30 test product baseplates and 30 comparator baseplates during their participation.

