18.6.2.1 Medical Advisor Safety Review

The Sponsor is responsible for ensuring all Serious Adverse Event (s) are provided to the Medical Advisor for review and discussion.

The Medical Advisor will be informed of the following:

- All serious adverse events related to the investigation product or clinical investigation and serious adverse device effects
- A device deficiency that could have led to a serious adverse event but did not because suitable action was taken, intervention had been made or because of fortunate circumstances
- New findings and/or updates in relation to already reported serious events

In addition, the Medical Advisor will receive lists of any reported AE's and ADE's related to the investigation product or clinical investigation, as defined by sponsor for a review of safety.

Correspondence, decisions and recommendations regarding safety in the Clinical Investigation from the Medical Advisor must be documented and saved electronically in the Sponsor File.

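### In section 18.6.1 the two end categories of the causality scale are defined by timing alone, so the scale is not ordered and its categories overlap

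*Combined protocol and SAP*

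**What the plan says.** Section 18.6.1 lists five levels of relatedness. The relevant definitions are:

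- 'Not related': "the event has no temporal relationship with the use of the test material or the procedures".
- 'Unlikely related' turns on relevance and cause instead of timing. It applies when "the relationship with the use of the test material seems not relevant and/or the event can be reasonably explained by another cause", with a rider that more information may be obtained.
- 'Possibly related': a weak link that cannot be fully excluded. Other causes may exist, and events that cannot be assessed default here.
- 'Probably related': "the relationship with the use of the test material seems relevant and/or the event cannot reasonably be explained by another cause", with the same rider.
- 'Definitely related/Causal relationship': "the event has a temporal relationship with the test material use/application or procedures".

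No other section adds a criterion to either end level or defines a temporal relationship.

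Relatedness is used in three further places. Section 18.2 makes an adverse event an adverse device effect when it is related to use of the device, and says it "should be marked as related or possibly related on the adverse event form". Section 18.6.1 requires adverse device effects to reach the sponsor within 10 days. Section 18.6.2.1 says "the Medical Advisor will receive lists of any reported AE's and ADE's related to the investigation product or clinical investigation".

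**The concern.** A causality scale should ask for more evidence at each step up, and each event should have one place on it. Here the end levels are judged on timing and the middle levels on other grounds. A stoma product is in use nearly all the time, so timing hardly separates device effects from coincidental illness.

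Safety is part of the stated aim (section 3) and adverse events are a safety endpoint (section 4.4.2). The trial is open-label and uses up to 15 sites in five countries. A site that follows the wording and a site that follows clinical judgement could grade the same event at opposite ends of the scale. Adverse device effect counts would then partly reflect how each site reads the definitions.

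**Working it through.** No figure in the plan needs reproducing and no power or rate calculation applies. The check sets the definitions beside the exposure pattern.

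**Step 1: what each level asks for (section 18.6.1).**

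| Level | Timing | Link to product | Alternative cause |
|---|---|---|---|
| Not related | must be absent | – | – |
| Unlikely | – | seems not relevant | and/or reasonably explains the event |
| Possibly | – | weak, not excluded | may exist |
| Probably | – | seems relevant | and/or does not reasonably explain the event |
| Definitely/Causal | must be present | – | – |

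The two end levels are complements on timing. The middle three do not mention timing, and the end two mention nothing else.

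**Step 2: order.** 'Probably related' needs a relevant link and/or no reasonable other explanation. 'Definitely related' needs neither. The criteria do not become stricter from the fourth level to the fifth.

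**Step 3: exposure.** Section 5.1.6 sets 42 ± 3 "days per test period, for a total of up to 90 days". It also says: "Subjects using 1-piece products are expected to change their products every day". Two-piece users are expected to use two baseplates every three days. The planned supply per product covers the longest period:

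- 1-piece: 45 products × 1 day = 45 days = 42 + 3.
- 2-piece: 30 baseplates × 3/2 days = 45 days = 42 + 3.

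The plan therefore assumes wear without planned gaps. The documents do not say so in words; this is inferred from the change pattern and the supply. There are two exceptions: any interval between V0 and V1, and the own-product time that section 4.1 allows after a period is stopped early.

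**Step 4: a test case.** Section 18.1 gives headache as an example of an adverse event. Take a headache on day 20 of a period, with an evident other cause.

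- It starts during product use, so on the literal wording the timing condition is present. 'Definitely related' is met and 'Not related' is excluded.
- Another cause reasonably explains it, so 'Unlikely related' is also met.

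One event fits the second-lowest and the highest level. The level most clinicians would consider first is closed.

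**Step 5: which product is assessed.** The scale refers to test material, which is not defined. Section 18.3 names the investigational device and the comparator separately. If test material means only the non-CE marked product, a coincident event in the comparator period could be 'Not related' while the same event in the test period could not.

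**Step 6: where the grade goes.** It determines adverse device effect status (18.2) and, with seriousness, serious adverse device effect status (18.4.1). It also determines the 10-day report (18.6.1), the lists to the Medical Advisor (18.6.2.1) and any summary by relatedness. It does not determine expedited reporting: all serious adverse events go to the sponsor within 24 hours (18.6.1) and to authorities and ethics committees, as applicable, within seven calendar days (18.6.2), whatever the grade.

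**The case against.** The strongest reply is that the top level carries its own label, 'Causal relationship'. Read with the causal definition of an adverse device effect in section 18.2, that label tells an investigator not to place a coincidental cold there, and 'Unlikely related' is available. This has force and will probably guide many sites. It does not cure the text, because the stated criterion beneath the label is timing alone, and 'Not related' has no label that rescues it.

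A second reply is that little depends on the grade. Section 11.1 only lists and summarises adverse events, if relevant. Section 11.4 concerns skin endpoints. Section 18.6.2.1 opens by providing all serious events to the Medical Advisor, and 18.6.2.2 adds ongoing review of all safety data. The literal reading would also send the Medical Advisor more events, so it would not by itself hide a signal. All of this stands and limits the reach of the point.

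A reader might go further and infer that every event during the trial is definitely related and none can be unrelated. The documents do not support that as a figure. It turns one reading of an undefined term into a percentage and passes over the label and the own-product allowance in section 4.1. A reader might also infer that a planned statistical comparison of device effects is compromised, but no such test is planned. Finally, section 18.2 might look like a rival two-level scale. It can equally be read as a cut-off at 'possibly' or above, with 'related' covering the two higher levels.

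**Conclusion.** The defect is in the stated rule and can be seen from section 18.6.1 alone: the end levels rest on timing, the scale is not ordered, and its levels overlap. The consequence for coincident events rests on two assumptions: that a temporal relationship includes onset during wear, and that wear is essentially uninterrupted while a subject is on product. The first is the plain reading of an undefined term. The second follows from the change pattern and supply in section 5.1.6.

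The reach is moderate and confined to safety classification: adverse device effect status, the 10-day report, the related-event lists and the descriptive summaries. Inconsistent grading between sites is a risk created by the wording; nothing in the documents shows how often it would occur. Section 7.1 provides for training in adverse event reporting but does not mention causality grading. The correction is cheap enough to be worth making before the first subject is enrolled.

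**What to change.** In section 18.6.1:

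1. Make 'Definitely related' stricter than 'Probably related': a temporal relationship, plus a plausible link to the product or procedure, plus no reasonable alternative cause. A shorter wording would serve if it puts a causal criterion beside timing and keeps the order.
2. Allow 'Not related' either when there is no temporal relationship or when another cause clearly explains the event and no plausible link exists.
3. State that the scale applies to the product worn at onset, test or comparator, and replace or define test material accordingly.

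In section 18.2, align the labels with the five levels by stating that an adverse device effect is an event graded possibly, probably or definitely related.

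The cost is wording in two sections, the help text on the adverse event form and a short item in site training. No extra data, visits or subjects are needed. If events have already been graded under the present wording, they would need to be reviewed again under the revised definitions.
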